9.1 Statistical Analysis

The primary analysis will focus on the feasibility outcomes. A mean or proportion of the feasibility measures will be calculated per cluster.

The same approach will be taken for the secondary outcomes with a per cluster analysis. We will calculate the mean difference between intervention and control groups by cluster with 95% confidence intervals in decisional conflict as our envisaged primary outcome as evidence towards proof of concept. Patient disposition and choice rates overall and stratified for the 4 distinct T-MACS risk categories (very low, low, moderate and high risk), choice adherence, adverse cardiac events and decision regret in the intervention group as well as physician satisfaction will be summarised using descriptive statistics in a cluster similar to the feasibility outcomes. The statistical analysis will be completed using SPSS version 23.

9.2 Sample Size:

No formal sample size calculation was conducted as part of this feasibility trial. Instead each cluster will have a dedicated 2-month recruitment period in each the control and intervention arm within the remit of our funding and available time line. We are estimating that each cluster should have about 200-300 eligible patients present to the department every month.

10) DATA MONITORING AND QUALITY ASSURANCE

To ensure collection of good quality data in accordance with Good Clinical Practice, remote monitoring visits will be undertaken monthly by the study co-ordinator. A separate monitoring plan will be provided to each site with specific instructions. Data monitoring will be done using the REDCap database that will be used throughout the study for data storage.

11) SAFETY CONSIDERATIONS AND ADVERSE EVENTS

An Adverse Event is any untoward medical occurrence, unintended disease or injury or any untoward clinical signs (including laboratory finings) in a study participant, which may or may not be related to the study intervention. This includes events related to the procedures involved in the study.

A Serious Adverse Event is an occurrence that has led to the death of a participant or serious deterioration in the participants' health.

Due to the nature of the study involving ED patients with suspected cardiac chest pain, it is to be expected that a proportion of the enrolled patients will have abnormal ECGs and/or abnormal (i.e. elevated) cardiac troponin levels as part of their routine care. Those will therefore not be recorded as an AE. Equally, we will not record acute myocardial infarction or revascularisation as a SAE in those who have opted to have serial troponin testing as these outcomes are to be expected in a proportion of the target population. However, those events will be recorded as SAE in participants who have opted to not pursue serial troponin testing and will be reviewed by an independent panel at the end of the study. Running the panel with preliminary results during the short 2-month period of the intervention arm will not be feasible.

SDM involves presenting patients with the possibility of "doing nothing" which in our study would equate to going home without serial troponin testing. While this intuitively sounds risky and potentially hazardous when thinking of patients identified having a moderate or high risk for ACS, mentioning the option is merely representative of real-life choice options. Offering choice should not be confused with actively advocating for a particular option. During development of the decision aid with patient groups, it was clear that they felt SDM should be offered to all patients, regardless of risk group. With ethical implications in mind, the intervention and training have been carefully designed to ensure that high-risk patients do not perceive that doctors are potentially allowing them to go home; rather, that they are being kept fully informed of their

Version 1.0

The University of Manchester

MANCHES

clinical status and the recommended treatment. Ultimately, the choice, as long as it represents an informed decision, does lie with the patient respecting their autonomy.

12) PEER REVIEW

This study has undergone peer review as part of the RCEM research grant application process and was deemed of sufficient academic quality to be awarded funding. Furthermore, the grant application had undergone peer-review prior to submission for the grant application. Since funding was awarded there has been further input from the NIHR Research Design Service improving in shaping this feasibility trial so it can provide the best possible information for a full-scale trial.

13) ETHICAL and REGULATORY CONSIDERATIONS

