5.2 Study Intervention and/or Procedures

We will undertake a stepped wedged cluster randomised controlled feasibility trial at two emergency departments (representing individual clusters): Manchester Royal Infirmary and the Royal Albert Edward Infirmary Wigan. With no site initially exposed to the shared decision making intervention, they will subsequently cross over after 2 months to intervention with a 1-month transition period for training purpose. The start date for each site will be randomly assigned.

MANCHES

Months	1	2	3	4	5	6	7	8
Trial set up								
Recruitment 1 st centre								
Recruitment 2 nd centre								
Data entry &verification								

Control group: Patients presenting with suspected cardiac chest pain receive diagnostic and treatment interventions according to local emergency department protocols based on T-MACS that have been verified for compliance with national or international guidance and are already in use at both hospitals as part of routine clinical care.

Transition stage: On completion of the recruitment time in the control arm the cluster will enter a designated 1-month transition stage. The purpose of this stage is twofold:

1) to allow installation of an update T-MACS Calculator with integrated SDM feature allowing to print off of the bespoke T-MACS Choice decision aid; and

2) physicians to undergo a designated training session on SDM including theory of the three talk communication model and demonstration of a shared decision making conversation using T-MACS Choice. This teaching session will be delivered as a face to face teaching session lasting 30-45 min by a member of the research team where possible. However, considering ongoing constraints on face-to-face teaching in light of the COVID-19 pandemic the teaching session where necessary will be provided as a live or on-demand online session allowing it to be readily accessible.

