Clinician training on SDM will be mandatory for all clinicians providing care in the respective ED's once T-MACS Choice is implemented to provide safe and effective clinical care and should be viewed as mandatory induction. Physicians who wish not to complete the clinician survey at the end of the training can opt out from participation on that survey. Nevertheless, once the training is completed, they are still able to recruit participants to the study. Similar to patients, clinicians during the recruitment period wishing not to participate in the research can opt-out from completing the clinician post encounter survey.

6.4 Randomisation:

The order in which the two clusters in this study will commence recruiting patients will be decided randomly. For that purpose, we will be using a computer-generated random number list.

6.5 Participants who withdraw consent [or lose capacity to consent]:

Participants can opt out and withdraw consent at any time without giving any reason, as participation in the research is voluntary, without their care or legal rights being affected.

If a participant decides to opt-out during the study we will use the data they have provide up to that point unless they indicate they wish for their collected data to be removed. From the point of opt-out we will collect no further data on that participant.

7) OUTCOME MEASURES

Primary outcome

The primary outcome is a composite of feasibility outcomes:

- Number of eligible participants per months recruitment period
- Recruitment rate
- Retention
- Percentage of missing data in secondary outcomes
- Ability to deliver physician training in shared decision making
- Ability to transition between control and intervention in transition time

Secondary outcomes

To determine if SDM is a successful intervention requires a multi-faceted approach. Therefore, as part of this feasibility study we will be collecting data on the envisaged outcome measures of the full scale stepped wedge trial to show feasibility of collecting these measures.

The envisaged primary outcome of the full-scale trial is a patient-related outcome of **decisional conflict**. This will be measured by the validated low literacy decisional conflict scale (LL-DCS) at the end of the ED

MANCHEST 1824

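### The by-site difference in decisional conflict is an uncontrolled before-after contrast and should not be offered as evidence towards proof of concept

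*Protocol*

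**What the plan says.** Protocol section 5.2 describes a "stepped wedged cluster randomised controlled feasibility trial at two emergency departments (representing individual clusters"). Neither site is exposed to SDM at first, and "they will subsequently cross over after 2 months to intervention with a 1-month transition period for training purpose". Section 9.2 gives the lengths: "each cluster will have a dedicated 2-month recruitment period in each the control and intervention arm". Each site therefore runs 2 months of control, 1 month of transition and 2 months of intervention, always in that order.

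The random element is when each site begins. Section 5.2 says "The start date for each site will be randomly assigned", and section 6.4 says "The order in which the two clusters in this study will commence recruiting patients will be decided randomly". The readable text gives no figure for the gap between the two starts. The timetable in section 5.2 runs in whole months from 1 to 8, but its shading is not legible.

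Section 9.1 makes the feasibility outcomes the primary analysis. For decisional conflict, measured by the low literacy decisional conflict scale (LL-DCS), it specifies the "mean difference between intervention and control groups by cluster with 95% confidence intervals in decisional conflict". The purpose given for this contrast is to serve "as evidence towards proof of concept". The summary at the front of the protocol also says, more loosely, that the outcome data will give some proof of concept. The proceed criteria in section 17 use the amount of missing LL-DCS data, not the difference between arms.

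**The concern.** A difference taken within one site, where control always comes first, has no concurrent comparison. Randomising which site starts first plays no part in it. Anything else that changes over those months, such as season, staffing, crowding or case mix, enters the difference in the same way as SDM does. Section 5.2 itself mentions continuing COVID-19 constraints, so a stable background cannot be taken for granted.

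Decisional conflict is the envisaged primary outcome of the full trial, and section 9.1 singles this contrast out for a between-group confidence interval and a proof-of-concept purpose. An interval that excludes zero could be taken as a sign that SDM works when it shows only that scores changed between two periods.

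**Working it through.** The protocol gives no standard deviation, intracluster correlation (ICC), cluster autocorrelation (CAC) or target effect, so there is no figure of its own to reproduce. There are three checks.

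**1. Can the design separate SDM from time?**

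Take a model with a site effect, a free effect for each calendar month and an SDM effect δ. A month in which only one site recruits is used up by its own month effect. Information on δ comes only from shared months, where

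site 1 mean − site 2 mean = site difference + δ × (x1 − x2),

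with x = 0 for control and 1 for intervention. To estimate δ, x1 − x2 must take at least two values over the shared months. With site 2 starting s months after site 1:

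| s (months) | Shared months (site 1 / site 2) | Values of x1 − x2 | δ estimable? |
|---|---|---|---|
| 0 | 1, 2 control/control; 4, 5 intervention/intervention | 0 only | no |
| 1 | 2 control/control; 5 intervention/intervention | 0 only | no |
| 2 | 4 intervention/control | 1 only | no |
| 3 | 4, 5 intervention/control | 1 only | no |
| 4 | 5 intervention/control | 1 only | no |
| 5 or 6 | none | none | no |

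In continuous time, a control/control overlap needs s < 2 and an intervention/control overlap needs s > 1. Both exist only for 1 < s < 2. A rank check of the design matrix agrees: on a quarter-month grid δ is estimable at 1.25, 1.5 and 1.75 months and at no other stagger from 0 to 5.75.

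Two other assumptions would identify δ. A linear time trend does so at every whole-month stagger from 0 to 6. Assuming no difference between the sites does so at s = 2, 3 or 4. The protocol states neither.

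**2. How often would drift alone give an interval excluding zero?**

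- Surveys: section 9.2 expects 200-300 eligible patients per site per month, so 400-600 over 2 months. At the 50% completion threshold in section 17, n = 200-300 per site and period.
- Standard deviation: 20 points (assumed).
- SE = 20 × √(2/n) = 2.00 at n = 200 and 1.63 at n = 300. The half-width, 1.96 × SE, is 3.9 and 3.2 points.
- With no SDM effect and a drift of d points, P(interval excludes zero) = P(Z > 1.96 − d/SE) + P(Z < −1.96 − d/SE).

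| Drift d (points, assumed) | n = 200 | n = 300 |
|---|---|---|
| 1 | 8% | 9% |
| 2 | 17% | 23% |
| 3 | 32% | 45% |
| 4 | 52% | 69% |

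**3. What would a patient-level interval cover if site means vary between periods?**

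The stable site effect cancels in a within-site difference, so only site-by-period variation matters. The true variance is SE² + 2 × ICC × (1 − CAC) × 20², and coverage is P(|Z| < 1.96 × SE/true SE).

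| ICC, CAC (assumed) | Added variance | n = 200 | n = 300 |
|---|---|---|---|
| ICC = 0 or CAC = 1 | 0 | 95% | 95% |
| 0.02, 0.9 | 1.6 | 90% | 88% |
| 0.05, 0.8 | 8.0 | 74% | 67% |

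Example, last row at n = 300: SE² = 2.667, true variance 10.667, SE ratio 2.0, coverage P(|Z| < 0.98) = 67%.

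**The case against.** The strongest reply is that little hangs on this contrast. The primary analysis is of feasibility. The phrasing speaks only of evidence towards a proof of concept. No proceed criterion uses the difference, and nothing in the protocol says that it will set the effect size of the full trial or that an interval excluding zero counts as success. All of this stands and keeps the severity modest. Use of the difference to size the full trial is a foreseeable risk, not a stated plan.

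A reader might infer that the planned interval is simply too narrow. The document does not support that. It does not say how the interval is computed, which an analysis plan may settle, and it gives no ICC. With ICC = 0 or CAC = 1 a patient-level interval has its full 95% coverage. The statement holds only conditionally: such an interval is too narrow for the SDM effect if outcomes vary between periods.

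A reader might also infer that the design can never separate SDM from time. That depends on the model. It holds at whole-month staggers with site effects and free month effects; a linear trend would remove the obstacle. The actual stagger cannot be read from the timetable.

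The drift values and the standard deviation are assumptions and say nothing about the drift that will occur at these two sites. They show only how sensitive the reading is.

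**Conclusion.** The point holds in a limited form. The by-site difference is a before-after comparison without a concurrent control, and the randomised start order does not protect it. With site effects and unrestricted month effects, SDM is not estimable at any whole-month stagger from 0 to 6. That result needs no assumed standard deviation or ICC, only that choice of model.

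The numerical consequences do rest on assumptions. With a standard deviation of 20 and 200-300 surveys per site and period, a drift of 1 to 4 points gives an interval excluding zero about 8% to 69% of the time when SDM has no effect. Coverage of a patient-level interval runs from 95% down to about 67% over the ICC and CAC values tried. Confounding with time is the main problem, and widening a sampling interval does not cure it. The claim attached to the analysis needs correcting; the feasibility objective and the proceed criteria are unaffected.

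**What to change.** In section 9.1, and in the matching phrase of the summary:

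- Remove the proof-of-concept claim.
- Label the by-site difference a descriptive, uncontrolled before-after comparison whose interval reflects patient sampling only.
- State that it will not be taken as evidence of an SDM effect or used as the effect size for the full trial.
- Present it also adjusted for T-MACS risk category and highest educational level, both already collected. Say that this reduces case-mix differences but does not remove confounding with calendar time.

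The cost is a few sentences and one regression. The downside is a weaker claim.

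A stagger strictly between 1 and 2 months is optional only. At 6 weeks the sites would share three two-week windows: control/control, intervention/control and intervention/intervention. With 50-75 surveys per site in each (200-300 divided by 4), the estimate is the middle site difference minus the average of the outer two. Its variance is 3 × 20²/m, so the half-width is 1.96 × √(1200/50) = 9.6 points down to 1.96 × √(1200/75) = 7.8 points, against 3.2-3.9 for the plain difference. Site-specific shocks in the single intervention/control window would still be confounded with SDM. This may be worth doing to rehearse the full trial's analysis, but it would not supply proof of concept.

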13.1 Approvals

NHS Research Ethics Committee and Health Research Authority (HRA) approval will be obtained before commencing this research study.

The study will be conducted in full conformance with all relevant legal requirements and the principles of the Declaration of Helsinki, Good Clinical Practice (GCP) and the UK Policy Framework for Health and Social Care Research 2017.

13.2 Risks

SDM involves presenting patients with the possibility of "doing nothing" which in our study would equate to going home without serial troponin testing. While this intuitively sounds risky and potentially hazardous when thinking of patients identified as having a moderate or high risk of ACS, mentioning the option is merely represents real life options. Offering choice should not be confused with actively advocating for a particular option. Ultimately the choice does and should lie with the patient, as long as it represents an informed decision as this is respecting their autonomy.

14) STATEMENT OF INDEMNITY

The University has insurance available in respect of research involving human subjects that provides cover for legal liabilities arising from its actions or those of its staff or supervised students. The University also has insurance available that provides compensation for non-negligent harm to research subjects occasioned in circumstances that are under the control of the University.

15) FUNDING and RESOURCES

Funding for this study was obtained from the Royal College of Emergency Medicine - RCEM Grant Number: G/2019/3.

16) PUBLICATION POLICY

This study will provide hardly needed evidence on the impact of SDM in UK emergency medicine and more specifically its role in the diagnostic process of patients presenting with suspected cardiac chest pain to the ED.

We will disseminate our findings in a multiple ways to maximise impact and accessibility to a wide audience including: (a) publication in peer reviewed academic journals, aiming for journals with high impact and a relevant target audience; (b) presentation at national and international scientific conferences; (c) publication on the trial and research group websites; (d) dissemination via press releases (including by Central Manchester University Hospitals NHS Foundation Trust; The University of Manchester; the NIHR

MANCH

Clinical Research Network); and (e) to promote public engagement, social media and blog posts. Participants that have indicated an interest in being kept informed will be updated as and when results will become available.

17) PROCEED CRITERIA

Depending on the outcome of the feasibility study the following proceed criteria have been agreed by the Trial Steering Committee:

Green	Yellow	Red
>50% of eligible patients	<25% under target recruitment	>50% under target recruitment
complete post-encounter survey	rate	rate
<20% of patient opt-out from 30	<25% of patient opt-out from 30	>30% of patient opt-out from 30
day follow up in intervention arm	day follow up in intervention arm	day follow up in intervention arm
<5% opt-out to follow up on	>5% opt-out to follow up on	>15% opt-out to follow up on
medical record/GP record review	medical record/GP record review	medical record/GP record review
at 30 days	at 30 days	at 30 days
<10% missing data on LL-DCS	<20% missing data on LL-DCS	>20% missing data on LL-DCS
<20% missing data on other	<30% missing data on other	>30% missing data on other
secondary outcomes	secondary outcomes	secondary outcomes

In case all feasibility outcomes are regarded 'green' we will proceed to a full scall trial with the currently envisaged protocol. In case of 'green' and 'yellow' outcomes adjustments will have to be made to the protocol based on the where the problem lies. A single 'red' criterion might be rectifiable with adjustments. However, in case of mainly 'red' criteria with no clear vision on how this could be rectified we will not proceed to a full-scale trial.

18) REFERENCES

